 Beginning with cycle 3, ADA/Immunogenicity sample collected every cycle, predose (ie, cycle 3, cycle 4, cycle 5, etc).

 Safety follow-up visit is to take place 30 (+ 3) days and 140 days ( $\pm 7$  days) after last dose. Long-term follow-up phone call at 6 months ( $\pm 1$  week) after last dose to collect information on survival, start of new therapies, and disease status.

[REDACTED]

 The EOT and SFU may be combined if the visit occurs 30 (+ 3) days after the last dose of AMG 404. **In addition, for subjects that continue treatment of AMG 404 in the extended treatment period only, assessments for ADA/immunogenicity and PK will not be collected at EOT and SFU visits.**

[figure not shown]
 Whole blood cytometry collections are required for Cohorts 1-6 only for receptor occupancy immunophenotyping. Last sample is collected cycle 3 predose (not required cycle 4 and beyond).

 Whole blood immunophenotyping collections are required for Cohorts 7-9 only for analysis of lymphocyte activation and exhaustion. Last sample is collected cycle 3 predose (not required cycle 4 and beyond)

[figure not shown]
[REDACTED]

**During the long-term follow-up phase serious adverse events suspected to be related to investigational products that the investigator becomes aware of will be reported to Amgen. After end of study, serious adverse events suspected to be related to investigational products will be reported to Amgen. Please refer to Section 10.2.3.1.1.3 for additional details.**

[figure not shown]
**Product:** AMG 404  
**Protocol Number:** 20180143  
**Date:** 20 May 2022

[figure not shown]
**Product:** AMG 404  
**Protocol Number:** 20180143  
**Date:** 20 May 2022

[figure not shown]
**Product:** AMG 404  
**Protocol Number:** 20180143  
**Date:** 20 May 2022

[figure not shown]
**Product:** AMG 404  
**Protocol Number:** 20180143  
**Date:** 20 May 2022

**Product:** AMG 404  
**Protocol Number:** 20180143  
**Date:** 20 May 2022

[figure not shown]

**Product:** AMG 404  
**Protocol Number:** 20180143  
**Date:** 20 May 2022

[figure not shown]

[figure not shown]
**Product:** AMG 404  
**Protocol Number:** 20180143  
**Date:** 20 May 2022

[figure not shown]
**Product:** AMG 404  
**Protocol Number:** 20180143  
**Date:** 20 May 2022

[figure not shown]
**Product:** AMG 404  
**Protocol Number:** 20180143  
**Date:** 20 May 2022

[figure not shown]
**Product:** AMG 404  

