#### 8.4.3.4 Immune-related Adverse Reactions

Adverse events following the administration of AMG 404 may represent an immunologic etiology. Based on clinical experience with other anti-PD-L1 therapies, these immune-related toxicities may occur shortly after the first dose to several months after the last dose of treatment and may affect more than one body system simultaneously. Early recognition and management are critical to reduce complications.

Most immune-related adverse events require adequate evaluation to confirm etiology or exclude other causes. Additional procedures or tests, such as bronchoscopy, endoscopy, or skin biopsy, may be included as part of the evaluation.

Based on the type and severity of the immune-related adverse event, withholding or permanent discontinuation of AMG 404, [REDACTED] may be required, in addition to treatment with corticosteroids and/or other therapies. Dose modification and toxicity management guidelines for immune-related adverse reactions are provided in [Table 13-2](#).

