###### 10.2.3.1.1.2 Serious Adverse Events

For Cohorts 1-█ the investigator is responsible for ensuring that all serious adverse events observed by the investigator or reported by the subject that occur after signing of the informed consent through the end of the **safety follow-up period of 140 days ( $\pm$  7 days) after last dose of IP** are reported using the Event CRF. █

█.

All serious adverse events will be collected, recorded and reported to the sponsor or designee within 24 hours **of the investigator's awareness of the event**, as indicated in Section 13.5. The investigator will submit any updated serious adverse event data to the sponsor within 24 hours of it being available.

**Since the criteria the CTCAE grading scale differs from the regulatory criteria for serious adverse events, if adverse events correspond to grade 4 CTCAE toxicity grading scale criteria (eg, laboratory abnormality reported as grade 4 without manifestation of life threatening status), it will be left to the investigator's judgment to also report these abnormalities as serious adverse events. For any adverse event that applies to this situation, comprehensive documentation of the event severity must be recorded in the subject medical records.**

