#### **10.2.3.1.1.3 Serious Adverse Events After the Protocol-required Reporting Period**

**If the investigator becomes aware of serious adverse events suspected to be related to investigational products after the protocol-required reporting period (as defined in Section 10.2.3.1.1.2) is complete, then these serious adverse events will be reported to Amgen within 24 hours following the investigator's awareness of the event on the Events CRF.**

**After End of Study, there is no requirement to actively monitor study subjects after the study has ended with regards to study subjects treated by the investigator.** However, if the investigator becomes aware of serious adverse events **suspected to be related to investigational product, then these serious adverse**

events **will be** reported to Amgen within 24 hours following the investigator's **awareness** of the event.

Serious adverse events reported outside of the protocol-required reporting period will be captured within the safety database as clinical trial cases and handled accordingly based on relationship to investigational product.

If further safety related data is needed to fulfill any regulatory reporting requirements for a reportable event, then additional information may need to be collected from the subject's records after the subject ends the study.

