The primary completion date is defined as the date when the last subject is assessed or receives an intervention for the final collection of data for the primary endpoint(s), for the purposes of conducting the primary analysis, whether the study concluded as planned in the protocol or was terminated early.

Progression Free Survival (PFS)

Progression-free survival is defined as the time from the first dose of IP until first documentation of radiological disease progression or death due to any cause, whichever occurs first. PFS will be censored at the last evaluable post-baseline tumor assessment date; otherwise, at first dose of IP. Progression will be based on RECIST v1.1.

Safety Follow-up visit

Upon permanent discontinuation from the study treatment for any reason, two safety follow-up visits are required. A safety follow-up visit will be performed approximately 30 (+3) days after the last administration of study drug, and also 140 days (± 7 days) after the last administration of AMG 404.

Serious Adverse Event

A serious adverse event (SAE) is defined as an adverse event that

- is fatal
- is life threatening (places the subject at immediate risk of death)
- requires in-patient hospitalization or prolongation of existing hospitalization
- results in persistent or significant disability/incapacity
- is a congenital anomaly/birth defect

- other medically important serious event

Study Day

Post study day: study day= (date - date of Study Day 1) + 1

Pre-study day: study day= (date – date of Study Day 1)

Study Day 1

It is defined as the first day that investigational product is administered to the subject. The day before Day 1 is referenced as Day -1.

t_{max}

The time takes to reach a maximum serum concentration of administered drug.

Treatment emergent AE

A treatment-emergent adverse event is any adverse event starting on or after the first administration of investigational product, as determined by the flag indicating if the AE started prior to first dose on the event eCRF and up to and including 140 days after the last IP dose date or end of the study, whichever occurs earlier.

Treatment related AE

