A treatment-related adverse event is any treatment-emergent adverse event that per investigator review has a reasonable possibility of being caused by the investigational product. In the unlikely event that the relationship is missing, the treatment-emergent event will be considered treatment-related and documented in a footnote of the treatment-related summary.

6. Analysis Sets

The analysis of all endpoints, unless noted otherwise, will be conducted on the Safety Analysis Set.

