9.6.2 Adverse Events

The most current version of the Medical Dictionary for Regulatory Activities (MedDRA) will be used to code all adverse events to a system organ class and a preferred term. The identification of adverse events of special interest is a continuous process. Events may be identified and documented as the safety profile of the drug is characterized. The severity of each adverse event will be graded using CTCAE version 5.0.

Tables will be provided for Subject incidence of all treatment-emergent, serious, treatment-related, those leading to withdrawal of investigational product, events of special interests and fatal adverse events by system organ class and preferred term in descending order of frequency. Where appropriate the tables will also be presented by worst grade.

Details of each treatment-emergent adverse event will be listed. Listings and/or narratives of any on-study deaths, serious treatment-emergent adverse, and grade 3 or higher treatment-related adverse, including adverse events leading to discontinuation of AMG 404, also will be provided should they occur.

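### The SAP closes the treatment-related window at exactly day 140 after the last dose, so some later events that the protocol collects cannot enter the treatment-related tables

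*SAP*

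**What the plan says.** SAP Section 5 (Definitions) sets two nested terms. A treatment-emergent event starts on or after first dose and "up to and including 140 days after the last IP dose date or end of the study, whichever occurs earlier". A treatment-related event is then drawn from that set: "A treatment-related adverse event is any treatment-emergent adverse event that per investigator review has a reasonable possibility of being caused by the investigational product". The default for a missing causality assessment has the same limit: "the treatment-emergent event will be considered treatment-related and documented in a footnote of the treatment-related summary".

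The protocol's collection rules reach further.

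- Sections 10.1.4 and 10.2.3.1.1.1 have all adverse events reported through 140 days (± 7 days) after the last dose. Section 10.2.3.1.1.2 sets the same "safety follow-up period of 140 days", with the same tolerance, for serious events.
- Section 10.2.3.1.1.3 adds a duty to report, on the Events CRF and within 24 hours, if the investigator "becomes aware of serious adverse events suspected to be related to investigational products after the protocol-required reporting period" is complete.
- The Table 3-1 footnotes repeat this for long-term follow-up: "During the long-term follow-up phase serious adverse events suspected to be related to investigational products that the investigator becomes aware of will be reported".

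On output, SAP 9.6.2 plans incidence tables for several categories, one of them treatment-related, and says "Details of each treatment-emergent adverse event will be listed". It provides no row, table or listing for related events that start after the cut.

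**The concern.** Treatment-related adverse events are named in the primary endpoint (Protocol 5.1, SAP 2.1). Under the SAP wording, an event that the investigator attributes to the drug and the site enters on the CRF is not treatment-related for analysis if it began on day 141 or later. The investigator's causality judgement is overridden by a date.

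The effect runs one way: dropping collected events can only lower the reported incidence. Late onset also matters for this drug class. Protocol 8.4.3.4 says that "these immune-related toxicities may occur shortly after the first dose to several months after the last dose of treatment", and Table 4-1 asks for monitoring after discontinuation because of late-onset hypothyroidism, colitis and pneumonitis.

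**Working it through.** The plan gives no figure to reproduce. The check sets the definitions beside the collection rules and adds simple date and rate arithmetic.

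**Inputs**

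- Treatment-emergent cut: day 140 after last dose, or end of study if earlier (SAP 5).
- Routine reporting: through day 140 ± 7, so the second safety visit may fall on days 133 to 147 (Protocol 10.1.4, 10.2.3.1.1.1).
- Long-term follow-up call: 6 months ± 1 week after last dose (Protocol 10.1.5). Taking 6 months as 183 days (an assumption), this is 183 ± 7, or days 176 to 190.
- Planned cohort sizes: about 40 in Cohorts 7, 8 and 9; about 20 in Cohorts 3, 4 and 6 (Protocol 11.1).

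**Does the end-of-study limb change anything?** A subject's end of study is the day of the last scheduled follow-up call (Protocol 10.1.6), which is after day 140. For a subject who reaches that call, the day-140 limb decides. The other limb can only shorten the window.

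**Tracing three related events**

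| Onset (days after last dose) | Collected under the protocol? | Treatment-emergent under SAP 5? | Treatment-related under SAP 5? |
|---|---|---|---|
| 139 | Yes, routinely | Yes | Yes |
| 144, second safety visit on day 146 | Yes, routinely | No | No |
| 150, serious | Yes, on the Events CRF, if the investigator becomes aware | No | No |

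**Length of the gaps**

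- Late-visit gap: 147 − 140 = at most 7 days, and only when the visit is late. With a visit on days 133 to 140 there is no loss of this kind.
- From day 140 to the call: 176 − 140 = 36 days, up to 190 − 140 = 50 days. Once the routine reporting period ends, only related serious events are reportable here, and only on investigator awareness.

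**Effect of one excluded event on subject incidence**

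- 40-subject cohort: 1/40 = 2.5 percentage points.
- 20-subject cohort: 1/20 = 5 percentage points.

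These are upper bounds for a single event. If the subject already counts in the row (for example, any treatment-related event), the row does not move. A specific preferred-term, grade or related-serious row might.

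**Where else could a late related serious event appear?** SAP Section 5 does not tie its definition of a serious event to treatment-emergence, and 9.6.2 names serious and fatal events as categories of their own without clearly limiting them to treatment-emergent ones. On-study deaths are listed with no such limit. SAP 9.1 has listings include all available data unless otherwise specified. Only the treatment-related tables exclude it with certainty.

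**The case against.** The strongest defence is that the window is a legitimate choice. The protocol leaves the definition of a treatment-emergent event to the SAP (Appendix 5), and 140 days equals the nominal length of routine reporting. After that, ascertainment is passive, and mixing passively and actively collected events in one incidence rate is questionable. The six-month call is for survival, new therapies and disease status; it is not an adverse event assessment. Late related serious events must still reach the sponsor within 24 hours, so oversight is not lost.

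Most of this stands, and it rules out several stronger readings that a reader might infer:

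- **That late related serious events vanish from all outputs.** The serious and fatal tables, the death listing and the general listings may still carry them.
- **That the SAP contradicts the protocol.** It does not, because the definition was delegated. Nor does late onset of several months conflict with day 140, which is itself about 4.6 months (140/30.4).
- **That the 36 to 50 days up to the call are lost surveillance time.** No scheduled adverse event assessment falls in that span once the second safety visit is done.
- **That the upper limit should simply be dropped for related events.** Treatment-related events would then no longer be a subset of treatment-emergent ones, so a related row could exceed its parent row. Onsets after new anticancer therapy would enter unmarked. So could reports made after the data capture system is closed, which arrive on paper forms.

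The defence does not answer two things. Events on days 141-147 collected at a late visit are actively ascertained, so the passive-reporting argument does not reach them. And for later related serious events, a reason to keep them out of the main rate is not a reason to leave them without a planned place in the treatment-related reporting.

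**Conclusion.** The point holds as a narrow reporting gap in a primary safety endpoint. Events starting on days 141-147 and collected at a late second safety visit, and related serious events on the Events CRF that start later still, cannot enter the treatment-related incidence tables. For the late-visit events the same cut also removes them from the treatment-emergent tables.

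The realised size is unknown, since the documents give no count, and it is probably small. Per event it is at most 2.5 points in a cohort of 40 or 5 points in a cohort of 20, on the assumption that the subject has no event already counted in that row. The direction is certain: the omission can only lower the reported incidence. It is worth correcting because the data are already collected and the change is cheap.

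**What to change.** 1. In SAP Section 5, end the treatment-emergent window at the later of day 140 and the date of the actual day-140 (± 7) safety visit, still bounded by end of study. The treatment-related window then moves with it.
2. Keep treatment-related events as a subset of treatment-emergent events. Add to SAP 9.6.2 a separate table row and a listing of serious events on the Events CRF that the investigator considers related and that start after that cut. Footnote them as passively collected, and mark any that began after new anticancer therapy.

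No new data collection is needed. The cost is a short change of SAP wording, a flag for onset after the cut, one extra output, and possibly slightly less favourable counts. Restricting the addition to the Events CRF avoids having to reconcile reports held only in the safety database.

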6.1 Safety Analysis Set

The safety analysis set will consist of all subjects who received at least one dose of AMG 404.

6.2 DLT Evaluable Set

The Dose Limiting Toxicity Analysis Set will contain DLT-evaluable subjects. The DLT window (ie, DLT-evaluable period) will be the first 28 days of AMG 404 treatment (starting cycle 1, day 1) for Cohorts 1-9. [REDACTED]

[REDACTED]

[REDACTED] The subject will be DLT evaluable if the subject has completed the DLT window as described above or experienced a DLT any time during the DLT window or has received at least 90% of the planned dose of investigational product(s) and is followed for at least 1 cycle. A subject will not be DLT evaluable if he/she drops out before completion of the DLT-evaluable period for reasons other than a DLT.

The primary assessment of DLT will include DLT-evaluable subjects from dose exploration cohorts. If data is available, assessment of DLT including DLT-evaluable subjects from dose expansion cohort may be considered.

6.3 Pharmacokinetic / Pharmacodynamic Analyses Set(s)

Pharmacokinetic Analyses Set

The PK Analysis Set will contain all subjects who have received at least 1 dose of AMG 404 and have at least 1 PK sample collected. These subjects will be evaluated for PK analysis unless the number of data points required for analysis is not enough, or significant protocol deviations have affected the data, or if key dosing or sampling information is missing.

7. Planned Analyses

7.1 Interim Analysis and Early Stopping Guidelines

Safety data will be reviewed on an ongoing basis. In the dose level review meetings, Amgen, in consultation with the site investigators, will review all available cumulative data by cohort prior to making dose determination decisions. Adverse events and DLTs observed in all subjects will be evaluated continually and fully integrated into all dose level review meetings and considered in all enrollment and dosing decisions.

Additional details regarding the dose review meeting are provided in sections 8.4.1 and 13.3 of the protocol.

There is a planned treatment of N~40 subjects at the RP2D with enrollment to cohorts 3 and 6. Additionally, there is a planned treatment of N~40 subjects at the RP2D with enrollment to Cohort 7, N~40 subjects enrolled to Cohort 8 and N~40 subjects enrolled to Cohort 9. For each of these cohorts (Cohort 3/6, Cohort 7, Cohort 8, Cohort 9), futility will be assessed after treating 15 and 25 subjects for at least 3 months. If the observed rate of responses is consistent with a lower than 15% response rate, enrollment and treatment at the RP2D may be terminated due to futility. For purposes of assessing

futility, a response is defined as an objective response per RECIST 1.1. The guidelines for early termination due to futility are as follows:

Number of Treated Subjects	Futility Termination Guideline
15	1 or fewer responders
25	4 or fewer responders
40	Enrollment to dose expansion cohort complete

If the true response rate is 15% then these termination guidelines result in a 69.4% probability of terminating dose expansion early with an expected sample size of 26.4 subjects. If the true response rate is 30% then there is a 90% probability of continuing enrollment to N~40 total subjects.

During this enrollment and treatment at the RP2D combining data from cohorts 3, 6, 7, 8 and 9 (up to 160 total subjects enrolled) and separately for each cohort including cohorts 10-13, Amgen will conduct evaluations of the ongoing subject incidence grade 4 or higher treatment-related adverse event rate to assess if the threshold for possible early termination of a cohort has been reached. If the threshold is met in the combined monotherapy data of expansion cohorts 3, 6, 7, 8, and 9 enrollment to all ongoing cohorts in the study, [REDACTED] will be halted pending review of safety data by the DLRT. If the threshold is met in a specific cohort, then enrollment to the specific cohort will be halted pending review of safety data by the DLRT. After receiving the DLRT recommendation, Amgen will choose to take one of the following actions.

When overall safety threshold exceeded in combined monotherapy data of expansion cohorts 3, 6, 7, 8, and 9:

- 1) Terminate the trial
- 2) Amend the protocol to potentially improve the benefit/risk for subjects (eg, increase safety monitoring, modify dose/schedule, mandate premedication)
- 3) Continue monotherapy dose expansion cohorts and other cohorts, as appropriate, without any changes

When cohort-specific safety threshold exceeded:

- 1) Terminate enrollment to the cohort
- 2) Amend the protocol to potentially improve the benefit/risk for subjects in the cohort of concern (eg, increase safety monitoring, modify dose/schedule, mandate premedication)
- 3) Continue enrollment to the specific cohort (as appropriate) without any changes

The methods for deriving the stopping boundaries overall for the combined monotherapy data of expansion cohorts 3, 6, 7, 8 and 9, or for within a cohort are described in Section 11.3 of the protocol with the stopping boundaries overall for the combined monotherapy data of expansion cohorts 3, 6, 7, 8 and 9 presented in [Table 7-1](#) and stopping boundaries for within a cohort presented in [Table 7-2](#). Operating characteristics with pre-specified batch size of 10 new subjects per batch are presented in [Table 7-3](#) (overall the combined monotherapy data of expansion cohorts 3, 6, 7, 8 and 9) and in [Table 7-4](#) (cohort with planned sample size of 40 subjects). The operating characteristics in [Table 7-2](#) and [Table 7-4](#) provide the probability of stopping the trial early for given hypothetical true rate of grade 4 or higher treatment-related adverse events, whereas the stopping criteria in [Table 7-1](#) and [Table 7-2](#) are based on situations where the empirical evidence would result in a posterior probability of $\geq 80\%$ that the true grade 4 or higher treatment-related adverse event rate is $\geq 20\%$.

Table 7-1. Stopping Boundary Overall for Combined Monotherapy Data of Cohorts 3, 6, 7, 8, and 9 With Posterior Probability of 80% and Grade 4 or Higher Treatment-Related Adverse Event Limit of 20%

Number of subjects	Stop study if observing this many subjects with grade 4 or higher treatment-related adverse events
10	≥ 4
20	≥ 6
30	≥ 9
40	≥ 11
50	≥ 13
60	≥ 15
70	≥ 18
80	≥ 20
90	≥ 22
100	≥ 24
110	≥ 26
120	≥ 28
130	≥ 31
140	≥ 33
150	≥ 35
160	Combined Monotherapy Data for Cohorts 3, 6, 7, 8 and 9 Complete

Table 7-2. Stopping Boundary for Enrollment within Cohorts 3, 6, [REDACTED] Individually With Posterior Probability of 80% and Subject Incidence of Grade 4 or Higher Treatment-Related Adverse Event Limit of 20%

Number of subjects treated	Stop cohort enrollment if observing this many subjects with grade 4 or higher treatment-related adverse events
5	≥ 3
10	≥ 4
20	≥ 6
30	≥ 9
40	Cohort Enrollment Complete*

* Enrollment for cohorts 7, 8, and 9 completes after n=40 subjects enrolled. Enrollment for cohorts 3, 6, [REDACTED] completes after n=20 subjects enrolled. [REDACTED] Early stopping rules (eg, at 5 or 10 treated subjects) are the same regardless of planned maximum sample size in a cohort.

Table 7-3 Operating Characteristics With Batch Size of 10 Subjects (Combining All Monotherapy Data of Expansion Cohorts 3, 6, 7, 8 and 9)

True grade 4 or higher treatment-related adverse event rate	Probability of early stopping of dose expansion	Average sample size of overall combined monotherapy data
0.10	2.1 %	156.9
0.15	12.7 %	143.1
0.20	46.4 %	105.8
0.25	86.4 %	58.7
0.30	98.9 %	31.5

Table 7-4. Operating Characteristics with Batch Size of 10 Subjects (Cohort-Specific Enrollment With Maximum Sample Cohort Size of n=40 Subjects)

True grade 4 or higher treatment-related adverse event rate	Probability of early stopping of cohort enrollment	Average cohort sample size
0.10	2.0%	39.5
0.15	9.7%	37.6
0.20	25.8%	33.9
0.25	47.8%	28.8
0.30	69.2%	23.4

